19.1.2 Endpoints and Hypotheses

Primary Safety Endpoints

The primary safety endpoint is the event rate of severe hypoglycemia and DKA from both Groups (1 & 2) during the first 6 months of study phase and second 6 months of continuation phase. The descriptive summary statistics will be presented by number of event and event rate (100 patient years) for severe hypoglycemia and DKA **separately**.

Descriptive summary (i.e. not statistically powered) for severe hypoglycemia and DKA events rates will be performed between the HCL and control arms for each age group (< 15 years, 15-25 years, and > 25 years), as well as the overall event rates.

Co-Primary Effectiveness Endpoints

The primary effectiveness endpoints consist of one-primary endpoint for each group.

Group 1 – Baseline A1C > 8%: Change in A1C (ΔA1C)

The primary effectiveness endpoints for the baseline A1C > 8% group is change in A1C from baseline to end of six-month treatment period, defined as A1C measured at the six-month treatment visit minus A1C measured at the randomization visit. The goal is to show superiority of the HCL Arm compared to the Control Arm in reducing A1C from baseline to end of six-month treatment period.

The hypothesis is mathematically expressed as:

H0: $\mu(HCL) \ge \mu(Control)$ Ha: $\mu(HCL) < \mu(Control)$

where $\mu(HCL)$ is the mean of change in A1C (%) with the HCL Arm, $\mu(Control)$ is the mean of change in A1C (%) with the Control Arm.

Group2 – Baseline A1C ≤ 8%: Time in Hypoglycemic Range

The primary effectiveness endpoint for the baseline A1C \leq 8% group is the time with SG below 70 mg/dL (3.9mmol/L) during the six-month study period, defined as percentage of SG below 70 mg/dL (3.9mmol/L) out of total number of available SG readings. The goal is to show superiority of the HCL Arm compared to the Control Arm in reducing daily time in hypoglycemic range. The hypothesis is mathematically expressed as:

CEP304 Clinical Investigation Plan CEP304DOC Revision H Page 138 of 182 Medtronic

H0: μ (HCL) ≥ μ (Control) Ha: μ (HCL) < μ (Control)

where $\mu(HCL)$ is the subject mean of time with SG below 70 mg/dL (3.9 mmol/L) in the HCL Arm, $\mu(Control)$ is the subject mean of time with SG below 70 mg/dL (3.9 mmol/L) in Control Arm.

Key Secondary Effectiveness Endpoints

Group 1 - Baseline A1C > 8%: Time in Hypoglycemic Range

The key secondary effectiveness endpoint for the baseline A1C > 8% group is the time with SG below 70 mg/dL (3.9mmol/L) during the six-month study period, defined as percentage of SG below 70 mg/dL (3.9mmol/L) out of total number of available SG readings. The goal is to show non-inferiority (with a non-inferiority margin of 2%) of the HCL Arm compared to the Control Arm. The hypothesis of non-inferiority is mathematically expressed as:

H0: $\mu(HCL) \ge \mu(Control) + 2\%$ Ha: $\mu(HCL) < \mu(Control) + 2\%$

where $\mu(HCL)$ is the subject mean of time with SG below 70 mg/dL (3.9mmol/L) in the HCL Arm, $\mu(Control)$ is the subject mean of time with SG below 70 mg/dL (3.9mmol/L) in the Control Arm.

Group2 – Baseline A1C ≤ 8%: Change in A1C (ΔA1C)

The key secondary effectiveness endpoint for the baseline A1C \leq 8% group is change in A1C from baseline to end of six-month treatment period, defined as A1C measured at the six-month treatment visit minus A1C measured at the randomization visit. The goal is to show non-inferiority (with a non-inferiority margin of 0.4%) of the HCL Arm compared to the Control Arm in reducing A1C from baseline to end of six-month treatment period. The hypothesis of non-inferiority is mathematically expressed as:

H0: $\mu(HCL) \ge \mu(Control) + 0.4\%$ Ha: $\mu(HCL) < \mu(Control) + 0.4\%$

where $\mu(HCL)$ is the mean of change in A1C (%) with the HCL Arm, $\mu(Control)$ is the mean of change in A1C (%) with the Control Arm.

CEP304 Clinical				
CEP304DOC	Revision	Н	Page 139 of 182	Medtronic

Rest of Secondary Effectiveness Endpoints

Group1+Group 2: Time in Hypoglycemic Range during Night

The secondary effectiveness endpoint is the time with SG below 70 mg/dL (3.9mmol/L) during Night. The goal is to show superiority of the HCL Arm compared to the Control Arm reducing time in hypoglycemic range during night. The hypothesis is mathematically expressed as:

H0: μ (HCL) ≥ μ (Control) Ha: μ (HCL) < μ (Control)

where $\mu(HCL)$ is the subject mean of time with SG below 70 mg/dL (3.9mmol/L) in the HCL Arm during night, $\mu(Control)$ is the subject mean of time with SG below 70 mg/dL (3.9mmol/L) in the Control Arm during the night.

Group1+Group 2: Time in Hypoglycemic Range during Day and Night

The endpoint of time in hypoglycemic range below 70 mg/dL (3.9mmol/L) will be evaluated for superiority in the combined Groups during day and night. The goal is to show superiority of the HCL Arm compared to the Control Arm in reducing time in hypoglycemic range. The hypothesis is mathematically expressed as:

H0: μ (HCL) ≥ μ (Control) Ha: μ (HCL) < μ (Control)

where $\mu(HCL)$ is the subject mean of time with SG below 70 mg/dL (3.9 mmol/L) in the HCL Arm, $\mu(Control)$ is the subject mean of time with SG below 70 mg/dL (3.9 mmol/L) in the Control Arm.

Group1+Group 2: Time in Target Range 70mg/dL (3.9mmol/L) - 180 mg/dL (10.0mmol/L) during Night

The endpoint of time in target range measures the time with SG in target range 70 mg/dL (3.9mmol/L) - 180 mg/dL (10.0mmol/L) during Night. The goal is to show superiority of the HCL Arm compared to the Control Arm in improving the time in target range. The hypothesis is mathematically expressed as:

H0: $\mu(HCL) \le \mu(Control)$ Ha: $\mu(HCL) > \mu(Control)$

where $\mu(HCL)$ is the subject mean of time with SG between 70mg/dL (3.9mmol/L) – 180 mg/dL (10.0mmol/L) range in the HCL Arm during Night, $\mu(Control)$ is the subject mean daily time with SG between 70mg/dL (3.9mmol/L) – 180 mg/dL (10.0mmol/L) range in the Control Arm.

Group1+Group 2: Time in Target Range 70mg/dL (3.9mmol/L) - 180 mg/dL (10.0mmol/L) during Day and

CEP304 Clinical I				
CEP304DOC	Revision	Н	Page 140 of 182	Medtronic

Night

The endpoint of time in target range measures the time with SG in target range 70 mg/dL (3.9mmol/L) – 180 mg/dL (10.0mmol/L) during Day and Night. The goal is to show superiority of the HCL Arm compared to the Combined Control Arm in improving the time in target range. The hypothesis is mathematically expressed as:

H0: $\mu(HCL) \le \mu(Controls)$ Ha: $\mu(HCL) > \mu(Controls)$

where $\mu(HCL)$ is the subject mean of time with SG between 70mg/dL (3.9mmol/L) – 180 mg/dL (10.0mmol/L) range in the HCL Arm during Day and Night, $\mu(Control)$ is the subject mean daily time with SG between 70mg/dL (3.9mmol/L) – 180 mg/dL (10.0mmol/L) range in the Control Arm.

Group1+Group 2: Change in A1C

The endpoint of change in A1C will be evaluated for superiority in the combined groups. The goal is to show superiority of the HCL Arm compared to the Control Arm in reducing A1C from baseline to end of six-month treatment period. The hypothesis is mathematically expressed as:

H0: $\mu(HCL) \ge \mu(Control)$ Ha: $\mu(HCL) < \mu(Control)$

where $\mu(HCL)$ is the mean of change in A1C (%) with the HCL Arm, $\mu(Control)$ is the mean of change in A1C (%) with the Control Arm.

CEP304DOC	Revision	Н	Page 141 of 182	Medtronic

CEP304 Clinical Investigation Plan

CEP304 Clinical In				
CEP304DOC	Revision	Н	Page 142 of 182	Medtronic

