The other secondary effectiveness endpoints are hierarchically ordered and will be evaluated in the fixed sequence from endpoint 1 to 5 during the first 6 months of study phase.

• Group 1 + Group 2: Time in Hypoglycemic Range during Night

The first secondary effectiveness endpoint is the time with SG below 70 mg/dL (3.9mmol/L) during Night. The goal is to show superiority of the HCL Arm compared to the Control Arm reducing time in hypoglycemic range during night.

• Group 1 + Group 2: Time in Hypoglycemic Range during Day and Night

The endpoint of time in hypoglycemic range below 70 mg/dL (3.9mmol/L) will be evaluated for superiority in the combined Groups. The goal is to show superiority of the HCL Arm compared to the Control Arm in reducing time in hypoglycemic range.

 Group 1 + Group 2: Time in Target Range 70mg/dL (3.9mmol/L) – 180 mg/dL (10.0mmol/L) during Night

The endpoint of time in target range measures the time with SG in target range 70 mg/dL (3.9mmol/L) – 180 mg/dL (10.0mmol/L) during Night. The goal is to show superiority of the HCL Arm compared to the Control Arm in improving the time in target range

 Group 1 + Group 2: Time in Target Range 70mg/dL (3.9mmol/L) – 180 mg/dL (10.0mmol/L) during Day and Night

The endpoint of time in target range measures the time with SG in target range $70 \, \text{mg/dL}$ (3.9 mmol/L) – $180 \, \text{mg/dL}$ (10.0 mmol/L) during Day and Night. The goal is to show superiority of the HCL Arm compared to the Control Arm in improving the time in target range

[figure not shown]
Group 1 + Group 2: Change in A1C

The endpoint of change in A1C will be evaluated for superiority in the combined Groups. The goal is to show superiority of the HCL Arm compared to the Control Arm in reducing A1C from baseline to end of six-month treatment period.

CEP304 Clinical				
CEP304DOC	Revision	Н	Page 41 of 182	Medtronic

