5.2.2 Secondary Effectiveness Endpoints

Key Secondary Effectiveness Endpoints

Group 1: Baseline A1C > 8%: Time in Hypoglycemic Range

- The key secondary effectiveness endpoint for the baseline A1C > 8% group is the time with SG below 70 mg/dL (3.9mmol/L) during the six-month study period, defined as percentage of SG below 70 mg/dL (3.9mmol/L) out of total number of available SG readings. The goal is to show non-inferiority (with a non-inferiority margin of 2%) of the HCL Arm compared to the Control Arm.
- The hypothesis of non-inferiority is mathematically expressed as:

H0: μ (HCL) ≥ μ (Control) + 2% Ha: μ (HCL) < μ (Control) + 2%

where $\mu(HCL)$ is the subject mean of time with SG below 70 mg/dL (3.9 mmol/L) in the HCL Arm, $\mu(Control)$ is the subject mean of time with SG below 70 mg/dL (3.9 mmol/L) in the Control Arm

Group 2: Baseline A1C ≤ 8%: Change in A1C (ΔA1C)

- The key secondary effectiveness endpoint for the baseline A1C ≤ 8% group is change in A1C from baseline to end of six-month treatment period, defined as A1C measured at the six-month treatment visit minus A1C measured at the randomization visit. The goal is to show non-inferiority (with a non-inferiority margin of 0.4%) of the HCL Arm compared to the Control Arm in reducing A1C from baseline to end of six-month treatment period.
- The hypothesis of non-inferiority is mathematically expressed as:
- H0: $\mu(HCL) \ge \mu(Control) + 0.4\%$
- Ha: μ(HCL) < μ(Control) + 0.4%
- where $\mu(HCL)$ is the mean of change in A1C (%) with the HCL Arm, $\mu(Control)$ is the mean of change in A1C (%) with the Control Arm.

Medtronic Business Restricted

CEP304 Clinical I				
CEP304DOC	Revision	Н	Page 48 of 182	Medtronic

Rest of Secondary Effectiveness Endpoints

1. Group 1 + Group 2: Time in Hypoglycemic Range during Night

The secondary effectiveness endpoint is the time with SG below 70 mg/dL (3.9mmol/L) during Night. The goal is to show superiority of the HCL Arm compared to the Control Arm reducing time in hypoglycemic range during night. The hypothesis is mathematically expressed as:

H0: μ (HCL) ≥ μ (Control) Ha: μ (HCL) < μ (Control)

where $\mu(HCL)$ is the subject mean of time with SG below 70 mg/dL (3.9 mmol/L) in the HCL Arm during night, $\mu(Control)$ is the subject mean of time with SG below 70 mg/dL (3.9 mmol/L) in the Control Arm during the night.

2. Group 1 + Group 2: Time in Hypoglycemic Range during Day and Night

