19.1.6 Analysis of Endpoints

Primary Effectiveness Endpoints:

Test will be tested against the 0.025 (one-sided) significance level and both have to be met to claim success for the associated Cohort.

Group1 – Baseline A1C > 8%: Change in A1C (ΔA1C)

The initial univariate analysis for this endpoint will be an analysis of covariance at six months. If the computed F-statistic has a one-sided P<0.025 (can be computed from the two-sided F-statistic by taking the square root and comparing to a one-sided t-statistic), the null hypothesis will be rejected in favor of the alternative, Other supporting analysis including multivariable modeling may also be done to support this finding.

Group2 – Baseline A1C ≤ 8%: Time in Hypoglycemic Range

The initial univariate analysis for this endpoint will be an analysis of covariance F-test at six months. If the computed F-statistic has a one-sided P<0.025 (can be computed from the two-sided F-statistic by taking the square root and comparing to a one-sided t-statistic), the null hypothesis will be rejected in favor of the

CEP304 Clinical	Investigatio			
CEP304DOC	Revision	Н	Page 144 of 182	Medtronic

alternative. Other supporting analysis including multivariable modeling may also be done to support this finding.

CEP304 Clinical I				
CEP304DOC	Revision	Н	Page 145 of 182	Medtronic

[figure not shown]

CEP304 Clinical Inv	estigation	n Plar	1	
CEP304DOC	Revision	Н	Page 146 of 182	Medtronic

CEP304DOC	Revision	Н	Page 147 of 182	Medtronic
	_			•

CEP304 Clinical Investigation Plan CEP304DOC Revision H Page 148 of 182 Medtronic

[figure not shown]
CEP304 Clinical Investigation Plan CEP304DOC Revision H Page 149 of 182 Medtronic

CEP304 Clinical Investigation Plan CEP304DOC Revision H Page 150 of 182 Medtronic

CEP304 Clinical Inv					
CEP304DOC	Revision	Н	Page 151 of 182	Medtronic	

[figure not shown]
CEP304 Clinical Inv				
CEP304DOC	Revision	Н	Page 152 of 182	Medtronic

[figure not shown]

CEP304 Clinical Inv					
CEP304DOC	Revision	Н	Page 153 of 182	Medtronic	

CEP304DOC	Revision	Н	Page 154 of 182	Medtronic	
1					
-					

CEP304 Clinical 1				
CEP304DOC	Revision	Н	Page 156 of 182	Medtronic

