Group1+Group 2: Time in Target Range 70mg/dL (3.9mmol/L) – 180 mg/dL (10.0mmol/L) during Night The endpoint of time in target range measures the time with SG in target range 70mg/dL (3.9mmol/L) – 180 mg/dL (10.0mmol/L) during Night. The goal is to show superiority of the HCL Arm compared to the Control Arm in improving the time in target range. The hypothesis is mathematically expressed as:

H₀: $\mu(HCL) \le \mu(Control)$

Ha: $\mu(HCL) > \mu(Control)$

Revision 3.0

Page 25 of 34

where $\mu(HCL)$ is the subject mean of time with SG between 70mg/dL (3.9mmol/L) – 180 mg/dL (10.0mmol/L) range in the HCL Arm during Night, $\mu(Control)$ is the subject mean daily time with SG between 70mg/dL (3.9mmol/L) – 180 mg/dL (10.0mmol/L) range in the Control Arm.

Group1+Group 2: Time in Target Range 70mg/dL (3.9mmol/L) – 180 mg/dL (10.0mmol/L) during Day and Night

The endpoint of time in target range measures the time with SG in target range 70mg/dL (3.9mmol/L) – 180 mg/dL (10.0mmol/L) during Day and Night. The goal is to show superiority of the HCL Arm compared to the Combined Control Arm in improving the time in target range. The hypothesis is mathematically expressed as:

H₀: $\mu(HCL) \le \mu(Controls)$

Ha: $\mu(HCL) > \mu(Controls)$

where $\mu(HCL)$ is the subject mean of time with SG between 70mg/dL (3.9mmol/L) – 180 mg/dL (10.0mmol/L) range in the HCL Arm during Day and Night, $\mu(Control)$ is the subject mean daily time with SG between 70mg/dL (3.9mmol/L) – 180 mg/dL (10.0mmol/L) range in the Control Arm.

Group1+Group 2: Change in A1C

The endpoint of change in A1C will be evaluated for superiority in the combined groups. The goal is to show superiority of the HCL Arm compared to the Control Arm in reducing A1C from baseline to end of six-month treatment period. The hypothesis is mathematically expressed as:

[figure not shown]
H₀: $\mu(HCL) \ge \mu(Control)$

[figure not shown]
Ha: $\mu(HCL) < \mu(Control)$

[figure not shown]
where $\mu(HCL)$ is the mean of change in A1C (%) with the HCL Arm, $\mu(Control)$ is the mean of change in A1C (%) with the Control Arm.

[figure not shown]
Note: Summary of all endpoints is presented with descriptive statistics with mean, SD, median, min and max values.

[figure not shown]

[figure not shown]

[figure not shown]

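### Does the Night time-in-target-range hypothesis really set HCL nights against Control whole days?

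*Protocol*

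**What the plan says.** The Night time-in-target-range endpoint pools the two A1C groups and is a superiority comparison. The Synopsis places it third among the remaining secondary endpoints: "The other secondary effectiveness endpoints are hierarchically ordered and will be evaluated in the fixed sequence from endpoint 1 to 5".

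Its hypothesis is written out in Protocol 5.2.2, Protocol 19.1.2 and SAP 7.9. Each statement has a title naming night, a sentence defining the endpoint and its goal, the null and alternative, and a closing clause that explains the two means. The definition and goal run together as "during Night. The goal is to show superiority of the HCL Arm compared to the Control Arm in improving the time in target range", with no separate period for either arm. The closing clause does separate them. In Protocol 19.1.2 it reads "range in the HCL Arm during Night, $\mu(Control)$ is the subject mean daily time with SG between 70mg/dL", and Protocol 5.2.2 has the same words. SAP 7.9 has "range in the HCL Arm during Night, $\mu(Control)$ is the subject mean daily time with SG". In none of the three is a night limit attached to the Control mean.

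Two neighbouring hypotheses are useful for comparison. For Night hypoglycemia, the Control mean in Protocol 5.2.2 "is the subject mean of time with SG below 70 mg/dL (3.9 mmol/L) in the Control Arm during the night", and Protocol 19.1.2 and SAP 7.9 agree. For Day and Night target range, SAP 7.9 has "range in the HCL Arm during Day and Night, $\mu(Control)$ is the subject mean daily time with SG".

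**The concern.** The closing clause is where the plan says what each symbol in the null and alternative stands for. Here the two symbols appear to cover different periods: nights for HCL, and something called *daily* for Control. If *daily* means the whole day, the contrast mixes the treatment effect with any difference between night and whole-day glucose control that exists without treatment. A superiority finding could then arise with no treatment effect at night, or a real effect could be hidden.

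The endpoint also sits in a fixed sequence. A distorted result in third place would affect whether the fourth and fifth endpoints (Day and Night target range, and change in A1C in the combined groups) are formally tested. Because the wording is the same in the Protocol and the SAP, comparing the closing clauses of the two documents would not reveal the slip.

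**Working it through.** The check is mainly a comparison of texts. The table shows the period attached to each mean in the four sensor-glucose hypotheses that pool the A1C groups. The pattern is the same in Protocol 5.2.2, Protocol 19.1.2 and SAP 7.9.

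| Hypothesis | Title and definition | HCL mean | Control mean |
|---|---|---|---|
| Hypoglycemia, Night | night | night | night |
| Hypoglycemia, Day and Night | day and night | no period given | no period given |
| Target range, Night | night | night | *daily*, no period given |
| Target range, Day and Night | day and night | day and night | *daily*, no period given |

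1. In every row the title and definition fix the period for the endpoint as a whole. The closing clauses are loose: only the first row labels both means.
2. The Control entry is the same in the last two rows. It is harmless in the Day and Night row and wrong in the Night row, which is what a clause carried from one hypothesis to its neighbour would produce.
3. *Daily* is weak evidence of a whole-day quantity. The goal of the Group 2 primary endpoint also uses the word, although that endpoint is defined as a percentage of available sensor readings. It may mean no more than averaged per day. The night limit is missing from the Control clause on either reading.
4. The Synopsis gives the endpoint a fourth time, with night in the title and definition and no separate clause for the means. There is no mismatch there.
5. Protocol 5.2 and SAP 7.2 base the sensor comparisons between arms on two weeks of CGM data at 3 months and at 6 months, without distinguishing the arms. That points to like-for-like derivation.

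A rough calculation shows why the reading matters. Let d be Control night time in range minus Control whole-day time in range, in percentage points. The literal contrast then equals the true night difference plus d. Inputs:

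- 140 per arm, from the cohort sizes in the Protocol (70 + 70 across the A1C groups).
- One-sided level 0.025, stated in Protocol 19.1.6 for the primaries and assumed here for this endpoint.
- SD of 12 to 20 percentage points in both arms, assumed. The visible text gives none.
- True night difference of zero, assumed.

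SE = SD × √(2/140), which is 1.43 for SD 12 and 2.39 for SD 20. The chance of claiming superiority is 1 − Φ(1.96 − d/SE).

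| d | SD 12 | SD 20 |
|---|---|---|
| 0 | 0.025 | 0.025 |
| +1 | 0.10 | 0.06 |
| +3 | 0.55 | 0.24 |
| −3 | below 0.001 | below 0.001 |

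So the literal contrast could mislead in either direction. Steps 1 to 5 show that it is not the contrast the plan sets up.

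**The case for a change.** The best case for acting is that the closing clause is the formal definition of what is tested, that it is wrong in every place where it appears, and that the endpoint gates two later ones. Correcting it needs a few words and touches nothing else. It can fairly be added that an obvious intention does not make a wrong sentence right.

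Much of this stands. The wording is wrong in three of three statements, and it departs from the plan's own pattern for Night hypoglycemia. It is not an artefact of text extraction either, because the same clause appears in separate sections of two documents.

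What does not follow is any consequence for the analysis. The clause cannot be read apart from the title, definition and goal above it, and these settle the period for both arms. To follow it literally, a programmer would have to derive one variable by two rules depending on the arm, for an endpoint named for night. Nothing else in the visible text suggests that. The sections on how the other secondary endpoints are analysed (Protocol 19.1.10 in the contents, and the later part of SAP 7.9) are not visible in the public copies. They are not counted here as missing, and the conclusion does not depend on them.

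**Conclusion.** The mismatch is real but clerical. The plan defines a night-against-night comparison, and one explanatory clause, repeated in three places, omits the night limit for Control. Putting it right would leave data collection, sample size, the test, the order of testing and the interpretation as they are. It does not justify a change to the plan, though the clause could be tidied if the documents are reopened for other reasons.

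The effect on the intended analysis is zero. The rejection probabilities in the calculation belong to a literal reading that the rest of the text rules out. They also rest on assumed SDs and night-versus-day differences, so they do not measure any risk in this trial. The conclusion assumes that the analyst applies the endpoint's title and definition to both arms, which is the ordinary reading.

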19.1.4 Randomization

For each Cohort (CSII, MDI or SAP) subjects will be randomized to HCL and Control Arm with a 1:1 ratio for greater than 6 years of age. 2-6 years of age subjects will automatically enter the HCL arm at the end of the run-in period.

The randomization will be stratified by the diabetes management therapies at time of enrollment and baseline A1c categories:

Diabetes Management Therapies(Cohort):

- CSII: Insulin pump therapy without CGM
- MDI
- SAP: Insulin pump therapy with CGM

Baseline A1C categories(Group):

- Baseline A1C ≤ 8%
- Baseline A1C >8%

Randomization will be based on a total of four strata per Cohort. In each stratum, block randomization will be used to divide potential patients into 2m blocks of size of 2n (block size can be different for each stratum). Please note that MDI group will be further stratified to equal number of subjects without CGM and with CGM. The clinical team and investigators are blind to the block size. Equal amount of subjects will be enrolled for Baseline $A1C \le 8\%$ group and Baseline A1C > 8% group.

CEP304 Clinical Investigation Plan				
CEP304DOC	Revision	Н	Page 143 of 182	Medtronic

